#### 4.0 Rationale

Complete is a three part Canadian observational research study program aimed at assessing the real life effectiveness of adalimumab in the management of Psoriasis, Psoriatic Arthritis and Ankylosing Spondylitis. The general aim of the program will be to identify and describe common elements in these three conditions with respect to the population at risk, comorbidities, burden of illness, prognostic factors and response to treatment in the real – life setting. This will have significant implications for educating physicians and patients in the assessment and identification of signs and symptoms that would prompt further investigation and possible earlier diagnosis and treatment of these conditions. The results will also have an important impact on the advancement of our understanding of the causal pathways for these conditions that could eventually lead to improved patient management. Therefore, in addition to addressing the objectives of the individual studies, the data obtained in the program will also be used to address this

#### general aim.

With respect to Psoriasis, adalimumab has been approved in Canada for patients with moderate to severe Psoriasis that are candidates for systemic therapy. For patients with moderate plaque Psoriasis adalimumab should be used for after phototherapy has been ineffective or inappropriate (Canadian Product Monograph). To date real — life observational data allowing the comparison of the effectiveness of adalimumab to topical agents and traditional systemic agents in patients failing current treatment have not been reported. There is also currently a knowledge gap with respect to the practice patterns and regional variation in the approach used by Canadian physicians in the management of patients with psoriasis.

Psoriasis presents a significant burden of illness through the physical and emotional manifestations that significantly affect the patient's quality of life as well as loss of productivity and direct and indirect costs. Assessment of the impact of different approaches to the management of moderate to severe psoriasis on these patient centric outcomes is therefore of paramount importance. Given that patient reported outcomes have a cultural and regional influence, the assessment of these outcomes in specific regions is also of high relevance and importance in the assessments of regional and global benefit – risk ratios.

An important consideration of Psoriasis is the fact that approximately 30% of the patients develop psoriatic arthritis (PsA). To date, there are no known predictors of progression to PsA among patients with psoriasis. In addition, it is known that triggers of psoriasis flare ups and disease progression have an environmental and genetic determinant. There is currently a knowledge and patient management gap with respect to the screening and detection of flare – up triggers or articular and extra articular signs and manifestations indicating progression of psoriasis or onset of PsA. There is therefore a general need for the assessment of these questions. However, given the potential genetic and environmental effect on the incidence of Psoriasis as well as it severity and progression,

these questions must be addressed at the regional level.

Finally, continuous monitoring of the safety of adalimumab is essential in order to assess whether the safety profile in a real – life setting is comparable to that expected on the basis of the data reported in controlled clinical trials and to ensure detection of any emerging signal.

The current study will address the above questions by conducting a prospective observational study of Canadian patients with moderate to severe psoriasis for whom change of current treatment is indicated. Patients will enter the cohort at the time that their treatment is changed and therefore patients treated with topical agents, traditional systemic agents and adalimumab will be eligible to be included in the study. The rationale for limiting the anti-TNF alpha agent to adalimumab is based on the prevention of within class variation with respect to clinical decision making, response to treatment and incidence of adverse events.

Follow up will be for 24 months and assessments will be as per routine clinical care and according to the judgment of the treating physician. However, follow up visits at approximately 3, 6, 12, 18 and 24 months will be recommended.

There will be a total of 660 patients with psoriasis enrolled from the clinics of 30 - 40 Canadian community dermatologists. The sample of clinicians will be a random proportional representation of the distribution of dermatologists and patients in Canada, thus allowing valid generalization to the Canadian population of psoriasis patients. In addition, enrollment of the patients in the study will be on the basis of change in current treatment due to lack of response or tolerability. The decision to change treatment must be reached prior to enrollment in and independently of the current study.

The study will assess clinical and patient reported outcomes that are relevant in the management of psoriasis and its impact on the patient's quality of life and societal burden

of illness. The design is that of a prospective observational study with its inherent biases including confounding by indication. Statistical methods including multi-variate models and propensity scores will be used to adjust between group differences with respect to prognostic baseline characteristics. Mixed effects models will be incorporated to compensate for unequal follow up and lack of precisely scheduled visits. The design and statistical analysis employed are therefore required and appropriate to produce a valid real – life assessment and comparison of the different modes for the management of psoriasis that are currently used in Canada.

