site including redness, itching, bruising, pain or swelling, stomach pain, nausea, headache and back pain. Rare side effects include malignancies, reversible lupus (without renal or CNS complications) and cytopenias. Therefore all patients treated with anti-TNF alpha agents must be monitored for serious infections and particularly tuberculosis before, during and after treatment. In addition monitoring of liver function, CBC and hepatitis profile are recommended.

The efficacy of adalimumab in controlling the symptoms of psoriasis has been demonstrated in several controlled clinical trials. Taken collectively the results of these studies that have been conducted on over 1600 patients with moderate to severe chronic plaque psoriasis who were candidates for systemic therapy or phototherapy have shown that adalimumab is efficacious in controlling the symptoms of psoriasis and in improving the quality of life of patients. More specifically, when compared to placebo or methotrexate, patients treated with adalimumab had a significantly higher therapeutic response rate, defined as achieving a PASI 75 and a Physician Global Assessment (PGA) value of  $\leq 1$  (indicating clear or minimal disease) at 16 weeks. The magnitude of effect versus placebo ranges from four-fold (79.6% versus 18.9%) to ten-fold (70.9% versus 6.5%) for PASI 75 and from 2.5 times (73.1% versus 30%) to 14.5 times (62.2% versus 4.3%) for PGA of clear or minimal. When compared to methotrexate the magnitude of effect is 2.2 times for PASI 75 (79.6% versus 35.5%) and 2.5 times for PGA of "clear or minimal" (73.1% versus 30%) 1.11-18,22-29. In addition, in one clinical trial patients crossed over to placebo after 33 weeks of treatment with adalimumab were significantly more likely to lose therapeutic response when compared to patients that were maintained on adalimumab up to week 52. With respect to quality of life, when compared to patients treated with placebo or methotrexate those treated with adalimumab in these controlled clinical trials have had better improvement in the Dermatology Quality of Life Index (DLQI) total score as well as in the disease severity, pain and pruritus subscales. Better improvement in the Physical and Mental subscales of the Medical Outcomes Study Short Form 12 (SF-12) was also observed for the adalimumab treated patients when compared

to placebo.

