recommended. Data obtained from more frequent visits or visits conducted at other time points will also be recorded in the study Case report Form. In fact, in order to avoid any bias and loss of information all information regarding the management of the patients during the 24 month follow up period of the study should be recorded in the study data collection forms. In addition to clinical data that will be ascertained by the treating physician, patient reported outcomes will also be ascertained through self administered questionnaires.

The following table describes the data that will be collected and the recommended timing of the assessments.

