| Compliance assessment                                              |       | X  | X  | X  | X  | X  |

- 1. Only changes from previous visit will be recorded
- 2. Only if used as part of routine care. For the baseline visit, historical data up to 6 months could be used.
- 3. Self Administered questionnaires. These could be completed at the physician's office, at home and sent by mail.
- 4. Relevant sections of the Case Report Form to be completed by rheumatologists or information must be obtained from the rheumatologists.

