#### Follow-Up Assessments (3, 6, 12, 18 and 24 months):

Given the observational nature of the study there no pre-determined protocol defined requirements for follow up schedules. Physicians will manage the patients in accordance with their current practice, their judgment and regional requirements in the case of reimbursement policies. However, investigators will be encouraged to follow the recommended schedule of assessments for the patients that are enrolled in the study. In addition, all information and data obtained at any visit occurring during the 24 follow up period of the study, including those that are outside of the recommended schedule, will be recorded in the study Case Report Form.

Laboratory tests are not required for the purposes of the study. However, when any tests are conducted as part of routine care or indicated by the condition of the patient, all results should be recorded in the study Case Report Form in physical changes section.

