#### 10.3 Sample Size Calculations

Sample size considerations are based on the primary objectives of the study, specifically the proportion of patients that achieve a PGA rating of "0" or "1" at 24 months of follow up.

The following data and assumptions were used to determine the sample size requirements for the study:

- In the Champion study after 16 weeks of treatment 73% of the patients treated with adalimumab, 30% of the patients treated with methotrexate and 11.3% of the patients treated with placebo achieved PGA values of 0 or 1 indicating clear or minimal disease.
- The Champion study was a randomized placebo controlled clinical trial that was based on a strict protocol not allowing any concomitant treatment and enrolling a very well defined patient population. In the current study we can assume that we will observe similar trends in the order of treatment effectiveness, by which adalimumab will be superior to traditional systemic agents, which will be superior to topical agents. However, due to case mix and use of concomitant medications the actual therapeutic effect and difference between groups may be more variable and lower than that observed in the CHAMPION study. We can therefore assume that due to patient profile, and in order to be conservative, that the observed proportion of patient achieving and maintaining a PGA≤ 1 at 6 months will be approximately 50%. A relative reduction of 20% (RR = 0.80) in PGA would be considered as the minimum acceptable for clinical importance. Therefore, the current study we should be powered to detect a 20% relative reduction between adalimumab and traditional systemic agents, and a similar difference between systemic and topical agents. It follows that if we assume that the proportion of patients treated with adalimumab that achieve PGA ≤1.0 at six months will be

50%, the proportion in the patients treated with traditional systemic agents will be 40% ( $\underline{RR}$ =0.8) and that in patients treated with topical agents will be 32% ( $\underline{RR}$  = 0.8).

• For an expected treatment group ratio of 1:1 for adalimumab: traditional systemic agents and topical agents a total of 360 (180: 180) patients will be required for 80% power and two tailed significance of 5%. Assuming a 25% attrition rate and allowing for 100 additional patients (10 per variable) in the multivariate analysis 660 (330:165:165) patients will be recruited.

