## 3.3 Unequal Time Periods for Assessments

Another problem with observational naturally occurring experiments is that patient assessments are not dictated by a strict protocol but as per the real – life setting they are based on routine clinical practice, the judgment of the physician and the availability of the patient. These create a problem with unequal duration of treatment and follow up and when assessments at defined time intervals are required. The mixed effects repeated measures

COMPLETE - PS Statistical Analysis Plan Version 3.0 July 23rd, 2015 Page 26 of 231

models that will be used in the current study resolve this issue. With these models the least square mean will be used to estimate the value of the variable at specific time points.

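### Mixed models handle irregular visits only if visit timing does not follow current disease state; otherwise the secondary change-score contrasts could be biased, by an unknown amount and in either direction

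*Protocol*

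**What the plan says.** Protocol Section 4.0 closes with the statement that "Mixed effects models will be incorporated to compensate for unequal follow up and lack of precisely scheduled visits". SAP 3.3 notes that assessments depend on routine practice, the physician and the patient's availability. It then says of the mixed effects repeated measures approach that the "models that will be used in the current study resolve this issue", with least-squares means giving the value at each time point.

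On how visits arise:
- Protocol 6.4 and 6.5.1 require no visits. Months 3, 6, 12, 18 and 24 are recommended for all cohorts alike.
- Protocol 6.5.1: "Physicians will manage the patients in accordance with their current practice, their judgment and regional requirements in the case of reimbursement policies".
- Protocol 6.5: "Data obtained from more frequent visits or visits conducted at other time points will also be recorded in the study Case report Form".
- Protocol 9.0 places each visit in the CRF section nearest in time, gives no window width, and supplies blank sections for additional visits.
- Protocol 3.0, on anti-TNF agents only: "Therefore all patients treated with anti-TNF alpha agents must be monitored for serious infections and particularly tuberculosis before, during and after treatment". No visit frequency is attached.
- Protocol Table 1, footnote 3, on the self-administered questionnaires: "These could be completed at the physician's office, at home and sent by mail". Section 6.5.1 adds follow-up of non-responders.

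SAP 3.11 compares the cohorts on change in BSA, PGA, DLQI, PASQ, BDI, the generic health survey (SF-12 in Table 1, SF-36 in SAP 3.11) and WLQ, by ANOVA or a mixed model. SAP 3.4 looks at the pattern of missing data. SAP 3.8 selects covariates from baseline differences.

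**The concern.** A likelihood-based mixed model gives valid means when the chance of being seen depends on scores already in the database. It does not when that chance depends on the patient's present, unrecorded state. If some patients come in because they are worse, their recorded scores over-represent bad periods, and the least-squares means carry that forward. If this happens to a different degree by cohort, the between-cohort contrast moves even when the treatments do not differ.

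Neither document states this condition. In the readable text nothing would detect a breach: there is no analysis window, no reason-for-visit item, no comparison of visit timing by cohort and no sensitivity analysis for timing. Baseline covariates and propensity scores cannot adjust for a visit process that runs after baseline. At stake are the secondary comparisons of disease activity, quality of life, depression and work limitation, in a report that would tell its readers the problem had been dealt with.

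**Working it through.** The documents give no figure for bias from visit timing, so there is none to reproduce. The check is a simulation with no true difference between cohorts.

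**Inputs from the documents.** 330 adalimumab and 165 comparator patients and 25% attrition (Protocol 10.3); baseline plus visits at months 3, 6, 12, 18 and 24 (Table 1); two-sided 5% (Protocol 10.3, SAP 3.1.1).

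**Assumed, because the documents give no values.** A score with total SD 1, higher being worse; half the variance between patients, half a fluctuation with correlation exp(−months/6); dropout unrelated to outcome; 80% or 60% of visit slots attended; an odds ratio (OR) for attending per SD of worse current state. The model has cohort-by-visit means and unstructured covariance. Each scenario used 600 to 3,000 runs. Bias is adalimumab minus comparator, so a negative value favours adalimumab.

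**Step 1: expected size by hand.** With attendance p, the mean among those seen shifts by about (1 − p) × ln(OR) SD. For OR 1.5, 2 and 3:
- p = 0.8: 0.2 × 0.405 = 0.08; 0.2 × 0.693 = 0.14; 0.2 × 1.099 = 0.22.
- p = 0.6: 0.4 × 0.405 = 0.16; 0.4 × 0.693 = 0.28; 0.4 × 1.099 = 0.44.

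The mixed model recovers what the patient's other records predict and leaves the rest. In step 2 the rest is about half.

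**Step 2: simulated month-24 contrast.**

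| Visit pattern | Attendance | Bias (SD) | False positives |
|---|---|---|---|
| Comparator follows current state (OR 1.5 / 2 / 3), adalimumab does not | 80% | −0.04 / −0.07 / −0.11 | 5.7 / 9.2 / 16.5% |
| Same | 60% | −0.09 / −0.15 / −0.22 | 12 / 21.5 / 41% |
| Both cohorts follow current state, OR 2 | 80% | 0.002 | 3.7% |
| Comparator follows its last recorded score, OR 3 | 60% | 0.001 | 6.5% |
| Comparator attends less when worse, OR 0.5 | 80% | +0.074 | 10.0% |
| Only adalimumab follows current state, OR 2 | 80% | +0.075 | 11.3% |
| All measured at the nominal date | all slots | 0.000 | 5.3% |

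With 600 runs, a true 5% is estimated to within 1.96 × √(0.05 × 0.95/600) = 1.7 percentage points. So 3.7, 5.7 and 6.5% are not distinguishable from 5%.

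**Step 3: visits moved rather than missed.** Let 25% or 50% of comparator visits fall in the worst month within ±2 months (±1 at months 3 and 6). Bias is −0.10 or −0.21 SD and false positives 18% or 52%. Check with the simulated standard error of 0.104: 0.1034/0.104 = 0.99 gives Φ(−0.97) + Φ(−2.95) = 0.17, and 0.208/0.104 = 2.00 gives Φ(0.04) = 0.52. If the correlation decays over 3 months instead of 6, the figures are −0.14 or −0.27 SD and 25% or 73%.

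**Step 4: a different model.** A DLQI-like score with between- and within-patient SD 4 (total √32 = 5.66), 248 and 124 patients (330 and 165 × 0.75) and a random-intercept model. Extra visits occur in 10 to 40% of bad months on topical treatment against 0 to 10% on adalimumab. The false difference is 0.11 to 1.05 points (0.11/5.66 = 0.02 to 1.05/5.66 = 0.19 SD), with 8 to 34% false positives. Calendar-date records alone give at most 0.05 points and 3 to 7%. This set-up can produce only one sign, by construction.

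**Step 5: two alternatives.** ANOVA, the other option in SAP 3.11, is also biased under the first pattern of step 2, by −0.04 to −0.17 SD. Dropping visits made because of worsening is not safe either. With the score of step 4, topical attendance of 60 to 80% and flare visits in 20 to 40% of bad months, a false difference of 0.3 to 0.9 points for adalimumab became 0.4 to 0.8 points against it, with 8 to 22% false positives.

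**The case against.** The strongest reply is that the documents do not describe the mechanism. No section says that patients attend when they flare. The reimbursement sentence names no cohort. The infection monitoring for anti-TNF agents carries no visit frequency, and Protocol 3.0 lists liver and kidney toxicity for traditional systemic agents, which could prompt monitoring just as well. One recommended schedule covers everyone. All of this stands. A reader might infer that adalimumab patients are seen by the calendar and the others when they are worse, so that the contrasts lean towards adalimumab. The documents do not support that: equal dependence cancels, the opposite pattern reverses the sign, and dependence on recorded scores is harmless.

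Second, the questionnaires have set months, a mail route and follow-up of non-responders, so part of the protection exists. That lowers the exposure. But Table 1 ties them to visit numbers, and nothing says that they go out when no visit takes place.

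Third, additional visits have their own CRF sections, and the table titles in SAP Section 5 run by Visits 1 to 6. The mock tables, including Table 53 for the mixed model, were not in the text available here and might hold a rule. That limits what can be said about extra visits. It does not remove selective attendance, or the placing of a symptom-prompted visit in the nearest slot.

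**Conclusion.** The point holds in conditional form. Protocol 4.0 and SAP 3.3 credit the mixed model with more than it can do, and the readable plan neither states the condition nor checks it. If visit timing follows current disease state differently by cohort, the secondary change-score contrasts could be biased by roughly 0 to 0.2 SD, with about 6 to 40% false positives, in favour of adalimumab or against it. The stronger visit-shifting assumptions of step 3 go beyond that range.

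These sizes rest on assumed attendance, odds ratios, correlation and variance split, and the documents supply none of these. They show what is possible and do not estimate what happened in this study. It would be wrong to conclude that the contrasts are biased, or that they favour adalimumab. The point makes no claim about the month-6 primary logistic analysis or the time-to-event analyses. It should be addressed before the secondary comparisons are interpreted.

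**What to change.** 1. State that the self-administered questionnaires (DLQI, BDI, SF-12, WLQ, patient global) are sent and completed at their Table 1 months from baseline for every patient, whether or not a clinic visit occurs, using the existing mail route and non-responder follow-up. Use these calendar-date records in the main mixed models.
2. Add a reason-for-visit item to each CRF visit section. Report visit frequency, timing and reason by cohort.
3. For BSA and PGA, which need a clinician, report the models with and without non-scheduled or worsening-prompted visits as sensitivity analyses. Do not make exclusion of worsening visits the main analysis: it selects on the outcome, through a label given by a physician who knows the treatment. Inverse-intensity weighting corrects only for dependence on recorded history, so it should not be presented as a cure.
4. In SAP 3.3, replace the claim that the issue is resolved with the condition: the mixed model is valid if, given the recorded data, visit timing does not depend on current unrecorded disease state.

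The cost is mailing by date, one CRF item and some extra analysis. If data collection has ended, visit dates are already on the CRF. Frequency and timing by cohort, the models with and without non-scheduled visits, and the corrected wording then need no new data.
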